CBC with Differential, Chemistry Panel, and Endocrine Testing	X		X C1-C2			Must be performed within 3 calendar days prior to dosing for all time points, except C1D1, which does not need to be repeated if performed within 7 days prior to the first dose. See Section 9.4.4 (Clinical Safety Laboratory Assessments) for list of laboratory tests.
Efficacy Assessments						
Clinical Breast Examination	X					Clinical breast examination by palpation of breast and axilla.

Table 2-2: On-treatment Pre-surgery (Neoadjuvant) Procedural Outline (Safety Run-in Phase and Randomized Phase; CA2097A8)

Procedure ^a	Neoadjuvant Treatment ^{b,c} Cycle 1-5 (1 cycle = 4 weeks)				Pre-surgery (within 7 days prior to surgery)	Notes ^d
	Day 1	Day 8	Day 15	Day 22		
Breast and Axilla Ultrasound (Preferred) or Mammogram	C2D22 (as clinically indicated)				X	Breast and axilla ultrasound (preferred) or mammogram to be done on C2D22 and within 7 calendar days prior to surgery. Every attempt should be made to image each participant using an identical imaging modality and acquisition protocol for all imaging time points.
Documentation of Actual Breast Surgery	See Notes.					Record actual type of BC surgery (ie, BCS, mastectomy) on day of or within 7 days after surgery.

Table 2-2: On-treatment Pre-surgery (Neoadjuvant) Procedural Outline (Safety Run-in Phase and Randomized Phase; CA2097A8)

Procedure ^a	Neoadjuvant Treatment ^{b,c} Cycle 1-5 (1 cycle = 4 weeks)				Pre-surgery (within 7 days prior to surgery)	Notes ^d
	Day 1	Day 8	Day 15	Day 22		
Study Drug						
Randomization	X					First dose to be administered within 3 calendar days following randomization (for Randomized Phase ONLY).
IRT Drug Assignment	X					Register the visit in the IRT for study drug allocation.

Table 2-2: On-treatment Pre-surgery (Neoadjuvant) Procedural Outline (Safety Run-in Phase and Randomized Phase; CA2097A8)

Procedure ^a	Neoadjuvant Treatment ^{b,c} Cycle 1-5 (1 cycle = 4 weeks)				Pre-surgery (within 7 days prior to surgery)	Notes ^d
	Day 1	Day 8	Day 15	Day 22		
Administer Nivolumab 480 mg (Safety Run-in Cohorts and Arms A and B)	X					To be administered Q4W IV. First dose to be administered within 3 calendar days following randomization. 
 • Randomized Phase: • Arm A and Arm B • Starting at C2D1 for Arm B

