4 OBJECTIVES AND ENDPOINTS

Table 4-1: Objectives and Endpoints

Objectives	Endpoints
Primary	

 Safety Run-in Phase: Number of participants with occurrence of DLT. 	
 DLT is defined as TEAE (graded according to the NCI CTCAE v5.0) that occurs during the first 4 weeks after treatment start and that meets specific criteria (see Section 5.1.2.1).

 Randomized Phase: To assess RCB 0-I rate by central assessment of palbociclib plus anastrozole with or without nivolumab in all participants with untreated primary BC ≥ 2 cm (ER+, HER2-). 	
 RCB 0-I rate assessed by central assessment at the time of definitive surgery. RCB is a continuous index combining pathological measurements of primary tumor (size and cellularity) and nodal metastases (number and size) defined by a point system at surgery (refer to Appendix 7 [RCB Methods]).
Secondary	

 To assess the safety and tolerability of palbociclib plus anastrozole with or without nivolumab. 	
 Incidence of AEs, SAEs, AEs leading to discontinuation, immune-related AEs, deaths, and laboratory abnormalities in all participants.

 To assess pCR rate by local assessment of palbociclib plus anastrozole with or without nivolumab in participants with untreated primary BC ≥ 2 cm (ER+, HER2-). 	
 pCR rate in all participants assessed by the local pathologist at the time of definitive surgery. 
 pCR, defined as no invasive residual disease in breast or lymph nodes (ie, ypT0/is, ypN0) in the current AJCC staging system.

 To assess ORR (clinical and radiological [ultrasound (preferred) or mammography]) by Investigator assessment and BCS rate of palbociclib plus anastrozole with or without nivolumab in participants with untreated primary BC ≥ 2 cm (ER+, HER2-). 	
 ORR is defined as the number of participants with a BOR of CR or PR divided by the number of randomized participants for each treatment group at the end of the study treatment period. BCS rate is defined as the number of participants who undergo BCS after completing the study treatments divided by the number of randomized participants for each treatment group.

Table 4-1: Objectives and Endpoints

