9.1.3 Clinical Response Assessments

For the purposes of this study, all clinical response assessments, including 1) clinical breast examination by palpation of breast and axilla, and 2) imaging assessment of breast and axilla via ultrasound (preferred) or mammography, will be assessed by the Investigator and performed locally. Every attempt should be made to image each participant using an identical imaging modality and acquisition protocol for all imaging time points. Tumor measurements should be

made by the same Investigator or Imager for each assessment, whenever possible. Tumor assessments for all participants should continue per protocol, even if dosing is delayed or discontinued. The longest diameter (LD) of the initial lesion(s) will be reported as the baseline measurement and used as reference to characterize the objective tumor response. The LD of the same lesion(s) will be measured during subsequent imaging studies.

A best overall response of stable disease requires a minimum of 49 days on study from the first dose of treatment.

Screening and on-study images should be acquired as outlined in [Section 2](#) (Schedule of Activities). Tumor assessments at other time points may be performed if clinically indicated.

Bone scans and other SOC imaging, including pathologic examination of suspicious lesions, may be acquired per local standards, as clinically indicated.

At the Sponsor's discretion, images may be collected for review.

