9.1.3.1 Objective Response Rate Assessed by Imaging

ORR will be assessed at the end of the neoadjuvant treatment prior to Surgery.

For the purposes of this study, tumor response assessments will be performed by bilateral breast and axilla ultrasound (preferred) or mammography. Changes in tumor measurements and tumor responses will be assessed by the same Investigator or designee. The timepoint of tumor assessments will be reported on the eCRF based on the Investigator's assessment.

Radiographic Response Assessments:

- Radiographic complete response: Disappearance of the target lesion.
- Radiographic partial response (PR): At least a 30% decrease in the LD of the target lesion taking as reference the baseline LD.
- Radiographic progression (PD): At least a 20% increase in the LD of target lesion taking as references the baseline LD or the appearance of one or more new lesions.
- Radiographic stable disease (SD): Neither sufficient shrinkage to qualify for PR nor sufficient increase to qualify for PD taking as reference the baseline LD.

Note:

- 1) Target lesions should be selected on the basis of their size (lesions with the longest diameter) and should lend themselves to reproducible repeated measurements. Up to 2 lesions in the breast may be identified as target lesions. Per this protocol, target lesion #1 must be ≥ 2 cm and, if selected, target lesion #2 must be ≥ 10 mm. A sum of the diameters of all target lesions will be calculated and reported as the baseline sum of diameters. The baseline sum of diameters will be used as a reference to further characterize any objective tumor regression in the measurable dimension of the disease. Lesions that meet the criteria for radiographically defined simple cysts should not be considered malignant lesions (neither target nor non-target) since

they are, by definition, simple cysts. Pathologic axillary lymph nodes are not to be designated at target lesions, and lymph node measurements are not to be included in the sum of diameters.

[figure not shown]

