- 2) Target Lesions that become too small to measure: all lesions recorded at baseline should have their actual measurements recorded at each subsequent evaluation, even when very small (e.g., 2 mm). However, sometimes lesions that are recorded as target lesions at baseline become so faint on imaging that the radiologist may not feel comfortable assigning an exact measure and may report them as being too small to measure. When this occurs, it is important that a value be recorded on the eCRF as follows:
 - If it is the opinion of the radiologist that the lesion has likely disappeared, the measurement should be recorded as 0 mm.
 - If the lesion is believed to be present and is faintly seen but too small to accurately measure, too small to measure should be indicated.
- 3) Assessments of partial response and complete response do not require confirmation. A best objective response of stable disease requires a minimum of 42 days on study from randomization to the date of the follow-up imaging assessment.

[figure not shown]
For further information please refer to [Appendix 8](#) (RECIST v1.1).

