#### **4.2.2 *Objective Response Rate***

Objective Response Rate (ORR) is defined as the number of randomized subjects who achieve a best response of complete response (CR) or partial response (PR) based on investigator assessments (using RECIST v1.1 criteria, by clinical or radiological) divided by the number of all randomized subjects. Best Overall Response (BOR) is defined as the best response, as determined by the investigator (using RECIST v1.1 criteria, by clinical or radiological), recorded between the

[figure not shown]
date of randomization and the date of objectively documented progression per RECIST v1.1 criteria, the date of surgery, or date of subsequent therapy, whichever occurs first. For subjects without documented progression or subsequent therapy before surgery, all available pre-surgery response designations will contribute to the BOR determination. Confirmation of response is not required due to the limited number of planned tumor measurement before surgery.

[figure not shown]

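### Protocol Table 2-2 makes the C2D22 scan both conditional and scheduled, and the SAP counts every unconfirmed pre-surgery response, so the per-arm radiological ORR depends on who is scanned

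*Protocol*

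**What the plan says.** **Schedule.** In Protocol Table 2-2, the on-treatment cell for breast and axilla ultrasound or mammogram reads "C2D22 (as clinically indicated". The note beside it carries no such condition: "Breast and axilla ultrasound (preferred) or mammogram to be done on C2D22 and within 7 calendar days" before surgery. Protocol 9.1.3 adds that "Tumor assessments at other time points may be performed if clinically indicated".

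**Which scans count.** Protocol Table 4-1 defines the endpoint by best response: "ORR is defined as the number of participants with a BOR of CR or PR divided by the number of randomized participants", at the end of the study treatment period. Protocol 9.1.3.1 says "ORR will be assessed at the end of the neoadjuvant treatment prior to Surgery". SAP 4.2.2 takes the best response between randomization and the first of progression, surgery or subsequent therapy. For participants without progression or subsequent therapy before surgery, "all available pre-surgery response designations will contribute to the BOR determination".

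**Confirmation.** Both documents waive it. The Protocol says "Assessments of partial response and complete response do not require confirmation", and the SAP says "Confirmation of response is not required due to the limited number of planned tumor measurement before surgery".

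**Setting.** The study is open-label and non-comparative (Protocol 7.3). Imaging is read locally by the investigator (Protocol 9.1.3). SAP 7.5.4 gives ORR per arm with exact 95% and 90% intervals and repeats the analysis on clinical assessment.

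**The concern.** A site following the cell may scan at C2D22 only the patients it is worried about. A site following the note scans everyone. Neither can tell from the table whether a skipped C2D22 scan is a deviation.

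Under the SAP rule this reaches the endpoint. A participant scanned at C2D22 can be counted a responder on that scan even if the pre-surgery scan no longer meets the criterion, and can also be called progressive earlier. A participant with the same course who is not scanned has neither possibility. Because investigators know the arm, the share scanned could differ between arms, and the ORR estimates would then partly measure scan frequency.

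There is a related gap. The only unconditional post-baseline image is tied to the date of surgery, and the follow-up schedule (Protocol Table 2-3) lists none. A participant who never has surgery and was not scanned at C2D22 has no scheduled post-baseline image, yet stays in the all-randomized denominator.

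**Working it through.** The visible text gives no assumed ORR and no power statement for ORR, so there is no figure of the plan's own to reproduce. The check has a textual part and two illustrations.

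**1. Was C2D22 meant to feed BOR?** With 4-week cycles, C2D22 is study day 28 + 22 = 50, which is 49 days after first dose. Protocol 9.1.3 requires 49 days from first dose before stable disease can be a best response. The match suggests that the scan was intended as a response time point.

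**2. How scan frequency enters ORR.** Let p be the share of randomized participants in response at the pre-surgery scan, q the share in response at C2D22 but not at the pre-surgery scan (or without that scan), and f the share scanned at C2D22. Leaving aside early progression,

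ORR = p + f × q.

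With p = 50% and q = 10% (assumed):

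| f | ORR |
|---|---|
| 0 | 50% |
| 0.5 | 55% |
| 1 | 60% |

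In Arm A or B (n = 40) the range is 20/40 (exact 95% CI 33.8 to 66.2%) to 24/40 (43.3 to 75.1%). In Arm C (n = 30) it is 15/30 (31.3 to 68.7%) to 18/30 (40.6 to 77.3%). If f is the same in every arm, this source of difference in scanning between arms disappears.

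**3. How large might q be?** This was simulated with 2,000,000 draws per scenario. All inputs are assumptions: true change in longest diameter at surgery with mean -30% and SD 25 points; change at C2D22 equal to 50, 70 or 90% of the final change; measurement error SD 8 or 12 points per scan; partial response as a decrease of at least 30%; and an increase of at least 20% at C2D22 closing the response window. A single pre-surgery scan gives an ORR of 50%.

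| Share of final change reached by C2D22 | Error SD | Best-of-two ORR | Gain, all v none scanned |
|---|---|---|---|
| 50% | 8 | 50.5% | 0.5 |
| 50% | 12 | 52.4% | 2.4 |
| 70% | 8 | 52.1% | 2.1 |
| 70% | 12 | 54.9% | 4.9 |
| 90% | 8 | 55.0% | 5.0 |
| 90% | 12 | 58.1% | 8.1 |

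Early progression at C2D22 removes at most about 0.05 points of responders in these scenarios.

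The gain scales with the difference in the share scanned. For 80% against 60% it is (0.80 - 0.60) × 0.5 = 0.1 points up to (0.80 - 0.60) × 8.1 = 1.6 points.

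A second model on the log scale (median change -30%, measurement SD 0.10 to 0.20, C2D22 change 50 to 100% of the final log change) gave a gain of about 1 to 10 points for all against none.

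**4. Missing images.** A participant not evaluable for lack of any post-baseline image cannot be a responder. Each one who would otherwise have counted costs 1/40 = 2.5 points in Arm A or B, or 1/30 = 3.3 points in Arm C.

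**The case against.** **Section 9.1.3.1 does not restrict ORR to one scan.** A reader might infer that the Protocol requires ORR from the pre-surgery scan alone and that the SAP departs from it. The text does not go that far. It says when ORR is assessed; Table 4-1 defines ORR by BOR, 9.1.3.1 itself speaks of a best objective response, and the 49-day minimum falls on C2D22. This stands. What remains is that the two documents do not state the same rule.

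**Differential scanning by arm is not shown.** A reader might also infer a spurious difference of up to 8 points between arms. That figure needs one arm fully scanned and another not at all, 90% of the shrinkage reached by week 7, and the larger error SD. The note schedules the scan for everyone, and the amendment history shows its timing was aligned with an on-treatment biopsy. Centring the assumed change on the 30% cut-off is also close to the worst case: at a mean of -60% the same simulation gives 0.3 to 4.6 points, even for all against none. This stands too.

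**The consequence is limited.** ORR is secondary, no between-arm ORR test is planned in the visible text, and the exact interval at 20/40 already spans 34 to 66%. RCB 0-I is read centrally and blinded.

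**The missing-image gap is partial.** The pre-surgery scan is unconditional. Protocol 9.1.3 says assessments continue after dosing stops and permits extra scans when indicated. Clinical breast examination is scheduled on Day 1 of each cycle. The gap therefore affects radiological ORR only, and keeping such participants in the denominator is a usual conservative choice.

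None of this removes the contradiction within the table row or the dependence that the SAP rule creates.

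**Conclusion.** The contradiction in Table 2-2 is plain, and under SAP 4.2.2 the per-arm radiological ORR depends on how often sites scan at C2D22 and, through Protocol 9.1.3, at unscheduled times. The direction is mainly upward with more scans; earlier detection of progression works the other way but is small in the simulation.

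The size cannot be known from the documents. The illustrative range is about 0.5 to 8 points at the extreme of all against none, and about 0.1 to 1.6 points for 80% against 60%. Both rest on the assumed shrinkage, timing and measurement error above. The effect falls on the estimate for each arm and on any informal reading of Arm A or B against Arm C. It does not touch the primary RCB 0-I endpoint or the clinical-examination ORR. The documents support neither a claim that the arms will be scanned differently nor a claim that ORR must rest on a single scan.

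The point is worth correcting because the ambiguity is avoidable, the readers are unblinded, and the correction is small.

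**What to change.** 1. **Protocol Table 2-2.** Reconcile the cell with its note so that C2D22 imaging follows one schedule for every participant in every arm. Deleting the parenthetical condition from the cell would do this, since the note already schedules the scan.
2. **Protocol 9.1.3.1 and SAP 4.2.2 and 7.5.4.** State the same rule for which time points enter radiological BOR, limited to the scheduled scans, and say how a progression seen on an unscheduled scan is handled in BOR.
3. **SAP 7.5.4.** Report by arm the number of post-baseline scans per participant and the number not evaluable for lack of a post-baseline image.

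An ORR based on the pre-surgery scan alone, or an added end-of-treatment scan, is not needed to resolve the point.

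**Cost.** One table cell, a sentence in each document and one summary table. No procedure is added beyond what the note already asks for. ORR may be slightly lower if unscheduled scans no longer count.

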Targeted PE, Measurements, Vital Signs, and ECOG PS	X	X	Weight, BP, HR, temperature, and ECOG PS. Targeted PE may include ocular examination, if clinically indicated.
AE Assessment (including SAEs)	X	X	Participants will be followed for treatment-related toxicities until these toxicities resolve, return to baseline, or are deemed irreversible. Note: All AEs will be documented for a minimum of 100 days after last dose of nivolumab for Safety Run-in Cohorts and Arms A and B, and for 30 days from the last dose of study treatment for Arm C.
Concomitant Medication Review	X	X	Record at each visit.
Subsequent Cancer Treatment	X	X	At each visit, record any new surgery, radiotherapy, and systemic cancer therapy given for the disease under study.
Laboratory Tests			
CBC with Differential, Chemistry, and Endocrine	X	X	Must be performed at FU1. If study drug-related toxicities persist, must be repeated at FU2. See Section 9.4.4 (Clinical Safety Laboratory Assessments) for list of laboratory tests to conduct.

Abbreviations: AE = adverse event; BP = blood pressure; CBC = complete blood count; ECOG = Eastern Cooperative Oncology Group; eCRF = electronic case report form; FU1 = follow-up visit 1; FU2 = follow-up visit 2; HR = heart rate; ██████████ IV = intravenous; PE = physical examination; ██████████ PS = performance status; SAE = serious adverse event; SOC = standard of care.

^a Participants must be followed for at least 100 days after last dose of nivolumab. FU1 should occur 30 days (± 7 days) from the last dose of any treatment (IV or oral whichever comes later). FU2 occurs approximately 100 days (± 7 days) from last dose of nivolumab. Both follow-up visits should be conducted in person.

^b Some of the assessments referred to in this section may not be captured as data in the eCRF. They are intended to be used as safety monitoring by the treating physician. Additional testing or assessments may be performed as clinically necessary or where required by institutional or local regulations.

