5.1.3 Safety Follow-up Period

Depending on the treatment arms, there may be up to 2 in-person safety follow-up visits. FU1 will occur 30 days from the last dose (± 7 days) of the study treatment (PO or IV; whichever occurs later) for all arms. FU2 occurs approximately 100 days (± 7 days) from the last dose of nivolumab for Safety Run-in participants and Arms A and B in the Randomized Phase.

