9.2.2 Method of Detecting AEs and SAEs

AEs can be spontaneously reported or elicited during open-ended questioning, examination, or evaluation of a participant. Care should be taken not to introduce bias when collecting AEs and/or SAEs. Inquiry about specific AEs should be guided by clinical judgement in the context of known AEs, when appropriate for the program or protocol.

All non-serious AEs (not only those deemed to be treatment-related) should be collected continuously during the On-treatment Pre-surgery (neoadjuvant) Period and for a minimum of 100 days following discontinuation of nivolumab. For participants randomized in Arm C, non-serious AEs should be collected for 30 days from the date of last dose.

Every AE must be assessed by the Investigator with regard to whether it is considered immune-mediated. For events which are potentially immune-mediated, additional information will be collected on the participant's eCRF.

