### **7.6.6 Adverse Events**

Adverse events will be summarized by treatment group.

The following analyses will be conducted using the 30 days safety window only:

- Overall summary of any AEs by worst CTC grade (1, 2, 3, 4, 5, not reported, total) presented by SOC/PT.
- Overall summary of any AEs presented by worst CTC grade (any grade, grade 3-4, grade 5) by SOC/PT. This table will be restricted to events with an incidence greater or equal to 5% in any treatment group.
- Overall summary of any non-serious AEs presented by SOC/PT. This table will be restricted to events with an incidence greater or equal to 5% in any treatment group.
- Overall summary of any AEs that required immune modulating medication by worst CTC grade (any grade, grade 3-4, grade 5) presented by SOC/PT.
- Overall summary of drug-related AEs by worst CTC grade (1, 2, 3, 4, 5, not reported, total) presented by SOC/PT.

The following analyses will be conducted using the 30 days safety window and repeated using the 100 days safety window:

- Overall summary of drug-related AEs by worst CTC grade (any grade, grade 3-4, grade 5) presented by SOC/PT.

A by-subject AE listing will be provided. A by-subject listing of any AE requiring immune modulating medications will also be provided.

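### The ±7-day visit windows let the last scheduled safety visit fall up to 7 days before the stated AE collection period ends, and no later contact is scheduled

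*Protocol*

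**What the plan says.** Protocol Table 2-3 sets the collection periods. For nivolumab recipients, footnote a states "Participants must be followed for at least 100 days after last dose of nivolumab", and the AE row adds "All AEs will be documented for a minimum of 100 days after last dose of nivolumab for Safety Run-in Cohorts and Arms A and B". The control arm gets a shorter period in that row: "and for 30 days from the last dose of study treatment for Arm C". Section 9.2.2 repeats the Arm C rule for non-serious events: "For participants randomized in Arm C, non-serious AEs should be collected for 30 days from the date of last dose". Section 9.2.1 does the same for SAEs.

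The visits are set separately. Footnote a of Table 2-3 says "FU2 occurs approximately 100 days (± 7 days) from last dose of nivolumab". Section 5.1.3 says "FU1 will occur 30 days from the last dose (± 7 days) of the study treatment", for all arms. FU2 applies only to the run-in and Arms A and B, so FU1 is the last visit in Arm C. The Synopsis, protocol Section 5.1 and SAP Section 2.1 use different wording: FU1 inside 30 days and FU2 roughly inside 100 days, each with the same tolerance.

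SAP Section 6.1 counts AEs to 30 or 100 days after the last dose of study treatment, depending on the analysis. For most of the general AE tables, SAP Section 7.6.6 specifies "The following analyses will be conducted using the 30 days safety window only". The SAE tables in Section 7.6.3 also use 30 days, and the immune-mediated AE tables in Section 7.6.8 use 100 days.

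**The concern.** A collection period stated as a minimum needs a contact at or after its end. Here the tolerance runs in both directions, so a visit that is fully on schedule can come a week too soon. Nothing planned afterwards closes the period, and Section 9.2.1 places no duty on investigators to go looking for events in people who have left the study. Wording that places the visits inside 30 and 100 days reads as a ceiling, where Table 2-3 sets a floor (nivolumab groups) or a full 30 days (Arm C).

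At stake is the completeness of the safety tables. The gap falls unevenly for participants who complete treatment on time. Arms A and B are seen again at FU2, well after the 30-day window has closed; Arm C is not. Surgery is due within 4 weeks of the last dose, so the uncovered week can contain surgery or early postoperative events.

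**Working it through.** The plan has no derived figure to reproduce, because the windows and periods are simply stipulated. Below, Day n counts from the relevant last dose, and study day n counts from the first dose.

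**Inputs**
- FU1: 30 ± 7 days after last study treatment. FU2: 100 ± 7 days after last nivolumab (Table 2-3, Section 5.1.3).
- Collection: 100 days after nivolumab; 30 days in Arm C (Table 2-3, Sections 9.2.1 and 9.2.2).
- Five 28-day cycles, with nivolumab on Day 1 of each cycle (from Cycle 2 in Arm B). Assumption: the last anastrozole dose counted as study treatment is on Cycle 5 Day 28.
- Surgery within 28 days of last dose (Table 2-2, footnote b).
- Arm C: 30 planned participants (Section 10.1).

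**Step 1: earliest compliant last visit.** FU1: 30 − 7 = Day 23, short by 7/30 = 23%. FU2: 100 − 7 = Day 93, short by 7/100 = 7%.

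**Step 2: participant completing on schedule.** Last nivolumab is on study day 28 × 4 + 1 = 113. Last study treatment is on study day 28 × 5 = 140.

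| Item | Calculation | Study day |
|---|---|---|
| FU1 | 140 + 23 to 140 + 37 | 163 to 177 |
| 30-day window ends | 140 + 30 | 170 |
| FU2 | 113 + 93 to 113 + 107 | 206 to 220 |
| 100-day nivolumab period ends | 113 + 100 | 213 |

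In Arms A and B even the earliest FU2 (206) lies beyond 170, so the 30-day window is covered. The 100-day period can end 213 − 206 = 7 days after the last visit. In Arm C the last visit can be on study day 163, which is 170 − 163 = 7 days short.

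**Step 3: when Arms A and B also miss the 30-day window.** Let g be the days from last nivolumab to last study treatment. Counting from last nivolumab, the earliest possible last visit is max(93, g + 23), and the window ends at g + 30. A shortfall needs 93 < g + 30, so g ≥ 64.
- Only the Cycle 5 nivolumab dose omitted: g = 140 − 85 = 55, covered.
- Cycle 4 and 5 doses omitted, oral drugs continued to the end: g = 140 − 57 = 83. The last visit can be on study day 163, again 7 days short.

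Section 7.1.1 allows oral drugs to continue when nivolumab is omitted. The omission limit in Section 8.1.1 is 10 weeks (70 days) with exceptions. Values of g from 64 to 70 are therefore possible within the limit, and larger ones under the exceptions. An Arm B participant who stops in Cycle 1 never receives nivolumab and has no date from which to count FU2.

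**Step 4: ceiling and illustration.** If all 30 Arm C participants came on Day 23 and nothing was collected afterwards, the loss would be 30 × 7 = 210 of 30 × 30 = 900 person-days. The documents give no distribution of visit dates. If visits fell evenly over the 15 permitted days (assumption), 7/15 = 47% would be early, with a mean shortfall of (1 + 2 + … + 7)/15 = 28/15 = 1.9 days. The range per participant is 0 to 7 days.

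**Step 5: surgery.** On-time surgery falls by Day 28. With FU1 on Day 23 and surgery on Days 24 to 28, Arm C has no scheduled safety visit after surgery.

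**The case against.** The strongest reply is that visit window and collection period are separate duties. Collection is a calendar obligation, no passage ends it at FU1 or FU2, and a site that stops collecting in Arm C on Day 23 breaches Sections 9.2.1 and 9.2.2. The release from seeking events in former participants does not itself shorten the period. This stands. A reader might infer that the protocol contradicts itself, but the text does not support that, since both rules can be met through an unscheduled contact. What the reply does not supply is that contact.

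A second reply is that the week around surgery is not wholly unobserved. Table 2-2 has AE assessment running continuously, an examination in the 7 days before surgery, and a record of the operation on the day or within 7 days after it. That lowers the likely loss. None of these, however, is set up as an AE contact closing Day 30.

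A third reply concerns consequence. A reader might infer a bias in the comparison against nivolumab. The study is declared non-comparative and the safety tables are descriptive; for the multiple-event analysis, SAP Section 7.6.11 rules out formal comparison. For exposure-adjusted rates, SAP Section 7.1.1 ends person-time at the last known alive date when follow-up is short. The incidence tables have no such adjustment, so possible under-recording in the side-by-side tables remains.

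**Conclusion.** The point holds as a weakness of the schedule. The permitted windows do not secure the minimum collection periods that the protocol states, by up to 7 days per participant. For participants who finish on schedule, the 30-day window is backed by a later visit in Arms A and B and not in Arm C. Arm C events on Days 24 to 30, including perioperative ones, may therefore be under-recorded in the AE and SAE tables.

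The 7-day figure is a maximum. It requires a visit at the early edge and no later contact; the actual loss cannot be determined from the documents. AEs leading to discontinuation or dose modification (SAP Sections 7.6.4 and 7.6.5) are essentially unaffected, because such events would not normally begin more than three weeks after all study drug has stopped.

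A reader might also infer that the gap in the 30-day window is confined to the control arm. Step 3 shows otherwise: it can arise in Arms A and B when g is 64 days or more, and for an Arm B participant who never receives nivolumab.

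**What to change.** Either of two changes is enough:
- Set the windows to 0/+7 days: FU1 on Days 30 to 37 after last study treatment and FU2 on Days 100 to 107 after last nivolumab. FU1 then also follows on-time surgery.
- Keep ±7 days, and require a documented AE contact on or after Day 30 or Day 100, as applicable, whenever the closing visit was early.

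Align the wording in Table 2-3, Sections 5.1 and 5.1.3, the Synopsis and SAP Section 2.1, and remove the phrasing that reads as a ceiling.

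The first option keeps the same visits and procedures but narrows the scheduling window from 15 days to 8. The second leaves the window alone and adds an occasional remote contact. Either is a cheap improvement.

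Two matters stay open and need their own reconciliation. First, the SAP's 100-day window (Section 6.1) runs from last study treatment, while FU2 runs from last nivolumab. On the full schedule that window ends on study day 140 + 100 = 240, which is 240 − 220 = 20 to 240 − 206 = 34 days after the present FU2. Second, FU2 has no starting date for an Arm B participant who never received nivolumab.
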